With the above mentioned background, we aim to do a retrospective analysis of participants who have undergone pancreatic resections, at our centre. The aim is to assess the ability of physiological parameters assessed by CPET, in predicting post-operative morbidity and mortality. This study also aims at evaluating and analysing a comparator group of participants who did not have CPET and assess their perioperative outcomes, in particular post-operative complications, with those who had CPET.

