3 THEORETICAL FRAMEWORK

4 RESEARCH QUESTION/AIM(S)

Objectives: To assess if pre-operative cardiopulmonary exercise testing is useful and effective in predicting at risk participants for post-operative morbidity and mortality, who undergo Whipple's surgery.

DATA ELEMENTS

1. Participant flow

Recruitment Details:

Participants for the study will be identified from a prospectively maintained database, by database search from April 2016 to March 2020, online records, clinical portal and Somerset cancer registry. Duplicates will be removed, cases will be screened.

This is a single centre study, to be done at, Royal Blackburn Hospital, East Lancashire Hospitals NHS trust, a District general Hospital in North of England. The study will be carried out in the department of General and HPB surgery, in liaison with Department of anaesthesia. This is the HPB referral centre for Lancashire and South Cumbria and incorporates participants referred for pancreatic surgery from three hospital trusts (Lancashire Teaching, University Hospital Morecambe Bay and Blackpool Teaching Hospitals).

Arm/Group Information:

The study will have two groups of participants, one who have undergone CPET pre-operatively and the other who have not undergone CPET.

Group 1 – Participants who have undergone CPET as a part of pre-operative assessment as well as P-POSSUM score calculation for predicting post-operative morbidity and mortality.

P-POSSUM is a scoring system for general elective and emergency surgeries which takes into account various physiological and operative parameters to calculate risk of morbidity and mortality in terms of percentages.

Group 2 – Participants who have not undergone CPET as a part of pre-operative assessment rather have only P-POSSUM calculated for predicting post-operative morbidity and mortality.

Period of Overall Study:

The study was conducted from February 2021 to March 2022. The database search was conducted and data collated. The study was conducted in one stage over a year.

Participants:

143 participants were recruited for the study during a period of 1 year. Out of 143 participants, 30 participants had undergone CPET as a part of pre-operative assessment.

2. Baseline Characteristics:

Baseline Analysis Population Information:

Data on baseline characteristics included age, sex, comorbidities, Rockwell frailty score, ASA grade, BMI.

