Data on study specific characteristics included dates of admission and discharge, diagnosis, details of surgery undergone, details of morbidity using Clavien-Dindo classification and mortality. Details of CPET and its measures as well as P-POSSUM scores were collated.

CPET specific data collected:

- 1) Exercise induced ST ischaemia- yes/no
- 2) VO₂ peak: actual and predicted
- 3) Anaerobic threshold:
- 4) VE/VCO₂:
- 5) Pulmonary function test- normal/ obstructive/ restrictive
- 6) Duration of pedalling bike
- 7) 30 day predicted risk

3. Outcome Measures:

Primary Outcome measures:

Primary outcome was measured in terms of CPET/P-POSSUM predicted mortality compared to actual 30 day mortality.

- In-hospital mortality
- 30 days
- 90 days

Secondary outcome measures:

Secondary outcome was measured in terms of CPET/ P-POSSUM predicted morbidity compared to actual morbidity (Clavien-Dindo grade 3 and above).

Morbidity in terms of:

- Post-operative pancreatic fistula
- Biliary fistula
- Delayed gastric emptying
- Bleeding
- Intra-abdominal collection
- Renal failure
- Cardiac complications
- Pulmonary complications
- Pulmonary embolism /DVT

The occurrence of morbidity and mortality were measured in terms of numbers and percentages. The calculated risk of morbidity and mortality by CPET and P-POSSUM are in terms of percentages, ranging from 0 to 100%, higher the percentage leading to worse outcome.

Statistical analyses overview:

The baseline characteristics were analysed using percentages and frequencies (mean, median, mode, standard deviation). Chi-square test was used to assess if the two study groups were

comparable. The p-value calculated was considered significant if <0.05 and confidence interval of 95%.

The study specific measures were analysed using parametric and non-parametric tests and binary logistic regression analyses to compare predicted to actual mortality and morbidity, between the participants who have had CPET and those who have not.

Univariate and multivariate analysis were done to assess if CPET measures could be used to predict occurrence of post-operative complications and morbidity.

4. Adverse Event information:

This was a retrospective review of a prospectively maintained database.

No adverse events were overcome during the time of the study

5. Limitations and Caveat:

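### Predicted versus actual mortality is framed as a CPET versus non-CPET contrast, which on that reading does not measure how well CPET predicts death; no accuracy measure or same-patient analysis is stated

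*Combined protocol and SAP*

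**What the plan says.** Section 2 (Rationale) gives the first aim: "The aim is to assess the ability of physiological parameters assessed by CPET, in predicting post-operative morbidity and mortality". It then adds a further one: "This study also aims at evaluating and analysing a comparator group of participants who did not have CPET", whose perioperative outcomes are to be compared with those of participants who had CPET.

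Under Arm/Group Information, Group 1 had CPET "as well as P-POSSUM score calculation for predicting post-operative morbidity and mortality". Group 2 had no CPET and "rather have only P-POSSUM calculated for predicting post-operative morbidity and mortality". P-POSSUM itself "takes into account various physiological and operative parameters to calculate risk of morbidity and mortality in terms of percentages". On numbers: "Out of 143 participants, 30 participants had undergone CPET as a part of pre-operative assessment".

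Under 3. Outcome Measures: "Primary outcome was measured in terms of CPET/P-POSSUM predicted mortality compared to actual 30 day mortality". The CPET items collected include a 30-day predicted risk.

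The Statistical analyses overview has three relevant sentences. A chi-square test checks whether the groups are comparable. Parametric and non-parametric tests are then used with "binary logistic regression analyses to compare predicted to actual mortality and morbidity, between the participants who have had CPET and those who have not". Last, univariate and multivariate analyses relate CPET measures to complications and morbidity; mortality is not named there.

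**The concern.** Predictive accuracy is about which of the tested participants die and whether their scores said so. A contrast between tested and untested participants asks something else. Group 2 has no CPET prediction, so moving from one group to the other changes both the tool and the people. The documents do not say how participants came to have CPET. Selection is therefore possible but not established, and a chi-square check can show imbalance without adjusting for it.

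At stake is the mortality part of the aim. If the sentence is followed on its between-group reading, the plan gives a result for the primary outcome that says nothing about CPET's ability to identify those who die. Section 8 (Results of the study) reports no mortality result, so nothing there fills the gap.

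**Working it through.** The plan states no power, effect size or mortality rate, so there is no figure of its own to reproduce here. The group share does reproduce: 30/143 = 21.0%, as stated in section 8, which leaves 143 − 30 = 113 without CPET.

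**Step 1. What each analysis sentence covers.**

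| Sentence in the overview | Outcome named | Comparison |
|---|---|---|
| Chi-square | none (baseline) | CPET vs no CPET |
| Tests and logistic regression | mortality and morbidity | predicted vs actual, CPET vs no CPET |
| Univariate and multivariate | complications and morbidity | CPET measures as predictors |

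Only the second names mortality. None names a discrimination measure, a calibration measure, or a comparison of the two tools in the same participants.

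**Step 2. The between-group reading.** The plan does not spell out a statistic. As an illustration take

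D = (observed − mean CPET risk) in Group 1 − (observed − mean P-POSSUM risk) in Group 2.

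Assumptions: true mortality m of 2%, 5% or 8%; both scores correct on average; CPET either useless (c = 0.50, everyone given risk m) or good (c = 0.80, logit-normal risk with SD 1.22, 1.25 and 1.27 on the logit scale at the three rates); selection multiplies the odds of death in Group 1 by an odds ratio (OR) of 0.5 to 2.

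With no selection (OR = 1), each bracket has expectation 0, so E(D) = 0 for either score.

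With selection and the useless score, E(D) = OR·o/(1 + OR·o) − m, where o = m/(1 − m). At m = 5% and OR = 2: o = 0.05/0.95 = 0.0526, doubled 0.1053, so 0.1053/1.1053 = 9.5%, and E(D) = 9.5 − 5.0 = +4.5 percentage points. For the good score the same shift is averaged over the risk distribution by numerical integration.

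| Assumed mortality | E(D), c = 0.50, OR 0.5 to 2 | E(D), c = 0.80, OR 0.5 to 2 |
|---|---|---|
| 2% | −1.0 to +1.9 points | −1.0 to +1.8 points |
| 5% | −2.4 to +4.5 points | −2.3 to +3.9 points |
| 8% | −3.8 to +6.8 points | −3.5 to +5.6 points |

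The ranges nearly coincide. On this reading D responds to selection and hardly at all to whether CPET discriminates.

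**Step 3. The within-group reading.** Suppose instead that death is regressed on the log-odds of predicted risk within Group 1. The expected slope is 1 for the calibrated c = 0.80 score and 0 for a score that varies but carries no information. That analysis would separate good from useless, so Step 2 does not apply to it. If the reading means only agreement of totals, it checks average calibration and a constant risk would pass.

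**Step 4. What 30 participants can show.** Expected deaths = 30m; P(no death) = (1 − m)^30.

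| Assumed mortality | Expected deaths | P(no death) |
|---|---|---|
| 2% | 0.6 | 0.55 |
| 5% | 1.5 | 0.21 |
| 8% | 2.4 | 0.08 |

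With a mean predicted risk of 5% (1.5 expected deaths), observed/expected with exact 95% limits would be 0 (0 to 2.31) for no deaths, 0.67 (0.02 to 3.44) for one, and 1.33 (0.16 to 4.41) for two.

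**The case against.** The strongest reply is that comparing predicted with actual mortality naturally pairs each person's risk with that person's outcome, and that the primary outcome definition says the same. Logistic regression of death on predicted risk would then be a real test of prediction (Step 3), and the zero contrast in Step 2 would follow from the statistic chosen and from assuming scores that are right on average. This stands as a limit on the point: the calculation applies to one reading only. It does not remove the gap, because on the other reading no accuracy measure is stated.

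It can also be said that neither aim asks for a contest between CPET and P-POSSUM. That is fair. The same-participant analysis is proposed because both predictions exist in Group 1 and the outcome is worded for both tools.

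A third reply is that 30 participants cannot settle mortality prediction under any analysis, and that section 5 (Limitations and Caveat) already calls the CPET group small. True, but small numbers limit precision; they do not turn a group contrast into a measure of accuracy.

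Three stronger readings are tempting, and the documents support none of them:
- A reader might infer that the plan has no predictive analysis of CPET at all. It has one, for complications and morbidity.
- A reader might infer that the comparator group is itself a mistake. It serves a legitimate further aim in section 2.
- A reader might infer that the CPET group was selected and the contrast is therefore biased. The route to CPET is not described.

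**Conclusion.** The point holds in limited form. The plan words its mortality analysis as a CPET versus non-CPET contrast. On the between-group reading, that contrast does not measure CPET's predictive accuracy: for observed minus predicted mortality, with scores right on average and no selection, the expected value is 0 at c = 0.50 and at c = 0.80 alike. On the within-group reading the analysis could be informative, but the plan names no measure that would make it so. The equality at zero does not depend on the mortality rate. The ranges under selection rest on the assumed rates (2% to 8%) and odds ratios (0.5 to 2).

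The consequence is confined to mortality. The anaerobic-threshold result in section 8 comes from within the CPET subgroup, concerns intra-abdominal collection, and does not depend on this contrast.

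**What to change.** 1. Reword the primary analysis so that, in the 30 Group 1 participants, the CPET 30-day predicted risk and the P-POSSUM mortality risk are each set against actual 30-day mortality in the same people. First confirm that the CPET figure is a mortality risk. Report observed/expected with an exact confidence interval for each tool. Because that ratio checks only the average, also list both predicted risks for each death against those of the survivors. Label the whole descriptive.
2. Keep the CPET versus non-CPET comparison for the further aim in section 2 only, and state that it is not evidence of CPET's predictive accuracy.
3. Optional: a c-statistic for Clavien-Dindo grade 3 and above in Group 1. Results are already known, so it must be labelled post hoc and exploratory.

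The cost is a rewording and a short re-analysis of variables already collated, with no new data. The drawback is that the mortality result is openly limited to 30 participants and, with the few deaths shown in Step 4, will be very imprecise.

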This was a retrospective review of a prospectively maintained database. The participants who underwent CPET was small compared to participants who did not. A prospective study with a large sample size is required to obtain more reliable results.

6. Certain Agreements:

All PIs are employees of Sponsor.

There is no specified results disclosure agreement between the PIs and sponsor.

7. Results Point of Contact

Name: Miss [name] (Principal Investigator)

Organization Name: East Lancashire Hospitals NHS Trust

[contact]

Email Id: [contact]

8. Results of the study

143 participants had Pancreatoduodenectomy during the study period. CPET was performed in 30 participants (21%). The participants' age was 67 ± 9 (Mean \pm SD). Forty participants (28.2%) had developed intra-abdominal collection (Clavien-Dindo III). In the CPET subgroup, Anaerobic Threshold (AT) ≤ 14 on CPET was a risk factor to develop intra-abdominal collection, according to univariate analysis (60% Vs 9%, p-value 0.02) and multivariate analysis (HR 3.5, 95% CI 1.6-657, p-value 0.02). Another significant risk factor was post-operative pancreatic leak (POPF) (40% Vs 22%, p-value 0.04).

By this study we concluded that participants who have Anaerobic Threshold ≤ 14 on CPET, are more likely to develop intra-abdominal collection requiring drainage after Pancreatoduodenectomy. This group of participants will be less likely to start chemotherapy early.

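### The AT result of 60% vs 9% cannot arise from the stated 30 CPET participants, and the report does not allow a reader to tell which figure is wrong

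*Combined protocol and SAP*

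**What the plan says.** Under Participant flow the document states: "Out of 143 participants, 30 participants had undergone CPET as a part of pre-operative assessment". The results section (data element 8, Results of the study) repeats the figure: "CPET was performed in 30 participants (21" per cent of the cohort. It then reports, for the CPET subgroup split at AT ≤ 14, that a low AT was a risk factor for collection, "according to univariate analysis (60% Vs 9%, p-value 0.02". No numerators, group sizes or count of usable AT values accompany the percentages.

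The statistical analyses overview (data element 3, Outcome Measures) describes methods in general terms: "The study specific measures were analysed using parametric and non-parametric tests and binary logistic regression analyses". For the CPET measures it adds: "Univariate and multivariate analysis were done to assess if CPET measures could be used to predict occurrence of post-operative complications and morbidity". Chi-square is named only for checking that the two study groups were comparable. None of these methods is linked to the AT result.

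Two neighbouring figures matter here. The overall rate is given as "Forty participants (28.2%) had developed intra-abdominal collection (Clavien-Dindo III" in a cohort described by "143 participants had Pancreatoduodenectomy during the study period". A pancreatic fistula (POPF) contrast of 40% vs 22%, p = 0.04, follows the AT sentence with no population named.

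**The concern.** AT exists only for participants who had CPET, so both AT groups must lie within the 30. Percentages from groups this small can take few values, so a reader can check whether the printed pair is attainable. It is not. The study's closing conclusion, that a low AT identifies participants more likely to develop a collection, rests on this comparison. As printed, at least one figure behind it is wrong or incompletely described, and a reader cannot rebuild the table.

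What is at stake depends on the cause. A one-point misprint would leave the association much as reported. Unreported omissions would mean that the result comes from fewer people than stated and could depend on who was omitted. An error in the 30 itself would also affect the participant flow.

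**Working it through.** **Inputs.** CPET subgroup 30 of 143 (Participant flow; Results). AT result 60% vs 9%, p = 0.02 (Results). Overall 40 collections, 28.2%; POPF 40% vs 22%, p = 0.04 (Results).

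**Step 1: is the 30 consistent with its own percentage?** 30/143 = 20.98%, printed as 21%. Yes.

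**Step 2: can groups totalling 30 give 60% and 9%?** Among sizes up to 30, a value rounding to 60% needs a group of 5, 10, 15, 20 or 25 (or all 30, leaving no comparator). The other group is then 25, 20, 15, 10 or 5. A value rounding to 9% needs a group of 11 (1/11 = 9.1%), 22 (2/22 = 9.1%) or 23 (2/23 = 8.7%). The two lists do not meet. From the other side, groups of 11, 22 or 23 leave 19, 8 or 7, whose nearest values to 60% are 11/19 = 57.9%, 5/8 = 62.5% and 4/7 = 57.1%. Truncation and rounding up also give no table at 30. The answer is the same if the percentages are read as the share with AT ≤ 14 by collection status.

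**Step 3: which totals fit, and does p = 0.02 choose among them?** Fisher is two-sided. Wald is univariate logistic regression, z = ln(OR)/√(1/a + 1/b + 1/c + 1/d), with a to d the four cell counts.

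| Total | Table | Fisher | Pearson | Yates | Wald |
|---|---|---|---|---|---|
| 16 | 3/5 vs 1/11 | 0.063 | 0.029 | 0.120 | 0.051 |
| 21 | 6/10 vs 1/11 | 0.024 | 0.013 | 0.045 | 0.028 |
| 26 | 9/15 vs 1/11 | 0.014 | 0.008 | 0.026 | 0.021 |
| 27 | 3/5 vs 2/22 | 0.030 | 0.008 | 0.045 | 0.021 |
| 28 | 3/5 vs 2/23 | 0.027 | 0.007 | 0.038 | 0.019 |
| 29 (8.3% rounded up) | 3/5 vs 2/24 | 0.024 | 0.005 | 0.033 | 0.017 |
| 30 (9% should be 8%) | 3/5 vs 2/25 | 0.022 | 0.004 | 0.029 | 0.015 |
| 30 (9% should be 10%) | 12/20 vs 1/10 | 0.017 | 0.009 | 0.027 | 0.023 |
| 31 (the 30 is wrong) | 12/20 vs 1/11 | 0.008 | 0.006 | 0.018 | 0.018 |

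Fisher check at 21, with 7 collections: (2310 + 120 + 330)/116280 = 0.024. Wald check at 28: OR = (3 × 21)/(2 × 2) = 15.75, ln = 2.757, SE = √(1/3 + 1/2 + 1/2 + 1/21) = 1.175, z = 2.35, p = 0.019.

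A p that rounds to 0.02 is therefore available with participants omitted (21 by Fisher; 26, 27 and 28 by Wald), with a misprinted percentage, and with a total of 31. For the last, 31/143 = 21.7%, which would print as 22%, not 21%.

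**Step 4: sensitivity, only if AT values are missing.** Start from 3/5 vs 2/23 and restore 2 participants adversely, as no collection with AT ≤ 14 or collection with AT > 14:

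- 3/5 vs 4/25: Fisher 0.068
- 3/6 vs 3/24: Fisher 0.075
- 3/7 vs 2/23: Fisher 0.068

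Wald gives 0.052 to 0.057 on the same tables. Uncorrected Pearson stays below 0.05: for 3/6 vs 3/24, χ² = 30 × (3 × 21 − 3 × 3)²/(6 × 24 × 6 × 24) = 4.22, p = 0.040. Favourable assignment gives Fisher 0.022 or less. These are bounds, not estimates.

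**Step 5: neighbouring figures.** POPF: 16/40 = 40.0% vs 23/103 = 22.3%, with 40 + 103 = 143, gives Fisher 0.039, so the whole cohort reproduces the printed result. Within 30 or fewer, the smallest crude p for 40% vs 22% is about 0.32 (4/10 vs 4/18, Pearson 0.318). Overall rate: 40/143 = 27.97%; 40/142 = 28.17%.

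**The case against.** The strongest reply is that this is a one-paragraph summary. Missing counts there do not show that the counts do not exist, a one-point slip would leave the association standing, and Limitations and Caveat already says that the CPET group was small and that a larger prospective study is needed. Most of this stands. However, a small group does not explain percentages that the group cannot produce.

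Four stronger readings are tempting, and the documents support none of them.

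- **Participants were dropped.** No exclusion or missing AT value is mentioned anywhere, and the number left out may be zero. The sensitivity bounds apply only if values are missing.
- **The cause must be either an omission or a misprinted percentage.** A wrong 30 is a third possibility. It is less likely because 30 appears twice and agrees with 21%.
- **The POPF result is also impossible.** It would be as a crude comparison within 30, but the text does not say it belongs to that subgroup, and the whole cohort reproduces it. What remains is an unnamed population.
- **The document promised counts for every contrast and broke that promise.** The sentence "The occurrence of morbidity and mortality were measured in terms of numbers and percentages" describes how outcomes were measured. It is not a commitment to give a numerator and denominator for each subgroup comparison.

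**Conclusion.** The inconsistency is established: 60% vs 9% cannot come from two groups that together make up 30 CPET participants under any of the rounding rules tried. It assumes only that the two percentages describe complementary groups within that subgroup, as the sentence says. The smallest repairs are one percentage point in one figure, one participant more than 30, or one participant fewer (two fewer under ordinary rounding). The p-value does not separate these, because the test is not named.

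A reader might infer that the AT association is spurious, and that goes too far. It may survive intact. What fails is the printed evidence for it, which cannot be verified as it stands. The correction should be made because the study's stated conclusion depends on this comparison. The POPF population and the one-participant gap between 28.2% and 28.0% are minor and change no inference.

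**What to change.** Check the database and correct whichever figure is wrong. In the results paragraph:

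- Give the count and denominator for AT ≤ 14 and for AT > 14, the number of CPET participants with a usable AT, and the test behind p = 0.02.
- Only if AT values are missing, say so, add a best-case/worst-case analysis assigning those participants to each AT group, and qualify the AT conclusion to match.
- If none are missing, correct the percentage or the 30, as the database shows.
- Name the population for the POPF contrast, and separate it from the CPET-subgroup sentence if it is a whole-cohort result.
- Print either 40/143 (28.0%), or 40/142 (28.2%) with one missing outcome declared.

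The cost is a database check and one rewritten paragraph, with no new data. The corrected result may look less favourable than the printed one.

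### The only adjusted estimate, a ratio of 3.5, does not fit its own 95% interval (1.6 to 657) and p-value (0.02) under a Wald interval, and its label HR is undefined

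*Combined protocol and SAP*

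**What the plan says.** Section 8 (Results of the study) gives one adjusted effect estimate. It comes from the subgroup of 30 participants who had CPET and relates an Anaerobic Threshold of 14 or below to intra-abdominal collection: "multivariate analysis (HR 3.5, 95% CI 1.6-657, p-value 0.02". The matching univariate result is 60% against 9%, p = 0.02. The section concludes that participants at or below this threshold "are more likely to develop intra-abdominal collection requiring drainage after Pancreatoduodenectomy".

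The methods are in section 3 (Outcome Measures), under the statistical analyses overview. The significance and confidence levels are given as "considered significant if <0.05 and confidence interval of 95" per cent. The only regression model named is in the phrase "binary logistic regression analyses to compare predicted to actual mortality and morbidity". The CPET analysis is described separately, without a model, covariates or effect measure: "Univariate and multivariate analysis were done to assess if CPET measures could be used to predict occurrence of post-operative complications and morbidity". The same section says that occurrence of morbidity was expressed as counts and percentages. Section 2 (Baseline Characteristics) adds: "Data on study specific characteristics included dates of admission and discharge". The abbreviation HR is not expanded anywhere.

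**The concern.** A ratio and its 95% limits are normally exponentiated from a coefficient and its standard error. The ratio then lies at the geometric centre of the limits, and the limits fix the p-value. Here 3.5 lies close to the lower limit of 1.6 and very far from the upper limit of 657, so at least one printed figure looks wrong.

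This is the only adjusted estimate in the document, and one of the two results behind the conclusion on Anaerobic Threshold; the other is the univariate comparison. Anyone who takes 3.5 into a review or a sample-size calculation may be using a value that its own interval does not support. A second problem compounds the first: the reader cannot tell whether the figure is an odds ratio or a hazard ratio.

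**Working it through.** **Inputs.** Ratio 3.5, limits 1.6 and 657, p = 0.02 (section 8); 95% confidence (statistical analyses overview). Assumptions: a two-sided test and a Wald interval on the log scale with z = 1.96. The document states neither.

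**Step 1: what the limits imply.**
- Centre = √(lower × upper) = √(1.6 × 657) = 32.42; ln 32.42 = 3.479.
- SE = ln(upper/lower) / (2 × 1.96) = ln(657/1.6) / 3.92 = 1.535.
- z = 3.479 / 1.535 = 2.27, so p = 0.023.
- With the limits varied within rounding (1.55 to 1.65 and 656.5 to 657.5), the centre is 31.9 to 32.9 and p is 0.022 to 0.025.

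The printed p-value is reproduced from the limits. The printed ratio is not: 32.42 / 3.5 = 9.3.

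**Step 2: keep 3.5 as the ratio and see what else must change.** ln 3.5 = 1.2528.

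| Kept with 3.5 | Calculation | Implied figures | Conflict with print |
|---|---|---|---|
| SE from the limits, 1.535 | z = 1.2528 / 1.535 = 0.82 | CI 0.17 to 71, p = 0.41 | both limits and p |
| Lower limit 1.6 | upper = 3.5² / 1.6 = 7.66; SE = ln(3.5/1.6) / 1.96 = 0.399 | p = 0.0017 | upper limit and p |
| Upper limit 657 | lower = 3.5² / 657 = 0.019; SE = ln(657/3.5) / 1.96 = 2.671 | p = 0.64 | lower limit and p |
| p = 0.02 | SE = 1.2528 / 2.326 = 0.539 | CI 1.22 to 10.1 | both limits |

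Rounding does not rescue any row. In the second row, a ratio of 3.45 to 3.55 with a lower limit of 1.55 to 1.65 gives an upper limit of 7.2 to 8.1 and p of 0.0010 to 0.0027. In the last row, p from 0.015 to 0.025 gives a lower limit of 1.17 to 1.28 and an upper limit of 9.6 to 10.5.

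**Step 3: lost decimal point in the upper limit.** An upper limit of 6.57 gives a centre of 3.24 and p = 0.001. An upper limit of 65.7 gives a centre of 10.3 and p = 0.014. Neither matches 3.5 and 0.02 together.

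**Step 4: 3.5 as the coefficient.** The log of the implied ratio is 3.479, and 3.46 to 3.49 over the rounding of the limits. It prints as 3.5 throughout. A coefficient of 3.5 beside exponentiated limits would therefore explain all the printed numbers.

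**Step 5: the label.** Logistic regression yields an odds ratio. A hazard ratio needs a time-to-event model with a time origin and a censoring rule, and the methods describe none. Admission and discharge dates were collected, but these do not in themselves date the onset of a collection. A hazard ratio is thus undescribed, though not contradicted.

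**The case against.** The strongest objection is that the interval may not be Wald. The document names no method, and in small samples profile-likelihood and exact intervals are asymmetric on the log scale. This is true, so 32.4 and the factor of nine are conditional figures. As an illustration, take assumed tables that reproduce 60% against 9% (the document gives no denominators). For 9/15 against 1/11, the conditional exact interval is 1.31 to 721 around 13.4. For 6/10 against 1/11, the profile-likelihood interval is 1.80 to 336 around 15. Both resemble the printed interval and centre well below 32.

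Neither comes near 3.5. For 3.5 to be the estimate, the upper arm of the interval on the log scale must be ln(657/3.5) / ln(3.5/1.6) = 5.235 / 0.783 = 6.7 times the lower arm. In the 6/10 example it is ln(336/15) / ln(15/1.80) = 1.5 times, and in the exact example ln(721/13.4) / ln(13.4/1.31) = 1.7 times. These tables are unadjusted and the adjusted model cannot be refitted from the document, so this is supporting evidence, not proof.

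The second objection is that, if 3.5 is the coefficient, the numbers do describe one estimate and only the label is wrong. That is correct, and it is why the mismatch is claimed only for 3.5 read as a ratio. A coefficient printed as HR beside exponentiated limits is still a reporting error.

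The third is that little depends on the figure. The conclusion is directional and quotes no effect size, the univariate result is separate, the primary outcome is unaffected, and section 5 (Limitations and Caveat) already concedes that the CPET group was small. All of this stands and limits the consequences. It does not excuse an inconsistent figure in the only adjusted result.

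**Conclusion.** The point holds, and the line is wrong as written. Under a Wald interval, a ratio of 3.5 fits neither the printed limits nor the printed p-value, while those two agree with each other (p = 0.023). Replacing the ratio alone reconciles the line, at about 32.4. Keeping 3.5 as a ratio requires at least two other printed figures to be wrong.

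Confidence is high for the mismatch under the Wald assumption and moderate for the suggested cause, a coefficient printed in place of its exponential. The document does not settle which figure is in error. If the limits and p-value are correct, the direction and nominal significance of the Anaerobic Threshold finding are unchanged, and the correction concerns the size and name of the effect. The label HR is undefined and has no described method behind it.

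**What to change.** Check the line in section 8 against the existing model output and print a point estimate, 95% interval and p-value that match one another. Do not presume which figure is wrong; a ratio near 32 is to be expected only if the limits and p-value are right and the interval is Wald. State how the interval was computed. Label the estimate by the model actually fitted: odds ratio if logistic. If it was a time-to-event model, describe that model in the statistical analyses overview.

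The cost is one line checked against output already held and, if needed, one sentence in the methods. No new analysis is required.
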